Preliminary results of this completed study indicate that TDF administered as the 300 mg tablet or oral powder formulation was well tolerated. No participant discontinued the study because of an adverse event. All treatment-emergent adverse events after administration of the oral powder and tablet were Grade 1 in severity. No serious adverse events or deaths occurred. Two participants discontinued the study by withdrawing consent. Treatment-emergent AEs were reported in 12 of 30 participants (40%, 18 events) after administration of the oral powder compared with 15 of 32 participants (47%, 29 events) after administration of the tablet. Headache, experienced by 4 participants (13%), was the most frequently reported treatment-emergent AE after The most frequently reported treatment-emergent AE after the oral powder. administration of the tablet were headache (6 participants, 19%) and dizziness (4 participants, 13%). Treatment-emergent AEs considered by the investigator to be related to study drug included flatulence (2 participants, 7 %), hot flush (1 participant, 3%) and increased ALT (1 participant, 2%); all related AEs were Grade I in severity and resolved without therapy. No AEs were considered related to study drug after administration of the tablet.

Peterson, et al. evaluated the safety of TDF 300 mg daily versus placebo for prevention of HIV-1 infection in women in a Phase 2 double-blind study conducted at 3 sites in West Africa.⁷ The study closed prematurely resulting in insufficient power to evaluate efficacy. In the primary safety analysis, with 428 person-years (p-y) of follow up, there was no significant difference in the rate of safety endpoints (defined as grade 2 or higher serum creatinine, grade 3 or 4 transaminase elevation, or grade 3 or 4 phosphate abnormality). Among the 368 participants on TDF, none had grade 3 or 4 transaminase elevation or grade 2 or higher creatinine. One TDF recipient had self-limited grade 3 phosphate.

Several other studies examining the safety and effectiveness of oral tenofovir as PrEP are underway or in later stages of planning. These include the following:

- The Bangkok Tenofovir Study (safety and efficacy of daily tenofovir to prevent parenteral HIV infection among injection drug users, CDC)
- Botswana TDF/FTC Oral HIV Prophylaxis Trial (Safety and Efficacy of Daily Oral Antiretroviral Use for the Prevention of HIV Infection in Heterosexually Active Young Adults in Botswana, CDC)

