3.2 Secondary Objectives

- To identify factors associated with product adherence, and whether these differ when women use one of three daily regimens of tenofovir (oral, vaginal, and dual use)
- To examine whether sexual activity or male condom use varies when women use one of three daily regimens of tenofovir (oral, vaginal, and dual use)
- To assess the timing of product use with sexual intercourse
- To determine the level of sharing of study products with non-participants (and to assess with whom products are shared)
- To characterize the differential safety profiles of three daily regimens of tenofovir (oral, vaginal, and dual use)

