Study site staff will report on study case report forms all AEs reported by or observed in enrolled study participants from the time of enrollment (random assignment) until study termination, regardless of severity and presumed relationship to study product. The Female Genital Grading Table for Use in Microbicide Studies (included in Appendix IV) will be the primary tool for grading adverse events for this protocol, with the exception of asymptomatic bacterial vaginosis which will not be a reportable AE. Adverse events not included in that table will be graded by the DAIDS AE Grading Table Version 1.0, December 2004. In cases where an AE is covered in both tables, the Female Genital Grading Table for Use in Microbicide Studies will be the grading scale utilized.

Participants will be encouraged to report to the study clinician any problems experienced by their male partners that might be potentially related to study product. If any such problems are reported, study staff should evaluate and document the occurrence and the Investigator of Record (or designee) should inform the PSRT, so that this information can be considered during routine PSRT safety data reviews. Should any concerns arise with regard to partner safety the PSRT will advise all study sites on appropriate action.

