8.3.3 Adverse Event Relationship to Study Product

The relationship of all AEs to study product will be assessed per the Manual for Expedited Reporting of Adverse Events to DAIDS (dated 6 May 2004), the tenofovir gel investigator's brochure, the Viread[®] package insert, and clinical judgment. Per the Manual for Expedited Reporting of Adverse Events to DAIDS, the relationship categories that will be used for this study are:

- *Definitely related*: adverse event and administration of study agent are related in time, and a direct association can be demonstrated with the study agent.
- *Probably related*: adverse event and administration of study agent are reasonably related in time, and the adverse event is more likely explained by the study agent than by other causes.
- *Possibly related*: adverse event and administration of study agent are reasonably related in time, and the adverse event can be explained equally well by causes other than the study agent.
- *Probably not related*: a potential relationship between administration of study agent and adverse event could exist, but is unlikely, and the adverse event is most likely explained by causes other than the study agent.
- *Not related*: the adverse event is clearly explained by another cause unrelated to administration of the study agent. Reportable events must have documentation to support the determination of "not related".

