10 STATISTICAL CONSIDERATIONS

10.1 Overview and General Design

This is a three-period, three treatment, multi-site, open label, crossover study. All the enrolled women will use all three treatments (i.e. oral TDF, tenofovir 1% gel, and a period of using both products), each in a separate period. The sequence of the three treatments will be randomly assigned. The total length of follow-up is 21 weeks: three periods of 6 weeks on treatment, each followed by a one-week washout period.

Each one-week washout period will be used to collect adverse events that may have resulted from product use during the previous period.

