10.2.2 Study Secondary Endpoints

Consistent with the secondary study objectives, the following secondary endpoints will be assessed:

- Proportion of women who report taking at least 90% of expected daily doses, frequency of use during the follow-up interval using an ordinal measure (5 categories of use, never to always); number of days product missed or not used during the previous week
- Frequency (ordinal measures) of sexual activity and male condom use
- Time interval between product usage and sexual intercourse; sequence of product use and sexual intercourse
- Reported sharing of study product; quantity of shared study product
- Grade 3 or higher toxicity for systemic and local effects as defined by DAIDS AE Grading Table Version 1.0, December 2004, or Grade 3 or higher genital infection, pain or epithelial lesion as defined by the Female Genital Grading Table for Use in Microbicide Studies which cannot be directly attributed to another cause, and judged as definitely, probably, possibly, or probably not related to the study gel, applicator, or study tablet

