10.5 Randomization Procedures

Randomization to product sequence will be stratified by site. Within each site, participants will be randomly assigned to one of six study sequences outlined in Table 15: Study Regimen below. In an unblinded trial, special care needs to be taken to assure that the study staff cannot control or guess assignment. The MTN Statistical and Data Management Center will coordinate the randomization procedures, which will be specified in the SSP Manual.

Table 15:	Stuc	dy Re	egimen	

	N	Period 1: 6 WEEKS	1 WK Wash -out	Period 2: 6 WEEKS	1 WK Wash- out	Period 3: 6 WEEKS	1 WK Wash- out
Sequence A	24	Oral		Vaginal		Oral + Vaginal	
Sequence B	24	Vaginal		Oral		Oral + Vaginal	
Sequence C	24	Oral + Vaginal		Oral		Vaginal	
Sequence D	24	Oral + Vaginal		Vaginal		Oral	
Sequence E	24	Oral		Oral + Vaginal		Vaginal	
Sequence F	24	Vaginal		Oral + Vaginal		Oral	

Assignment to end of study period non-intensive PK sample timing will correspond to product sequence randomization for simplicity. For the intensive PK cohorts at domestic sites, the end of study period sample timing will require a second randomization which will be stratified within each of the two sites.

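### The only safety endpoint for comparing regimens depends on an unblinded causality judgment, which exposes it to attribution bias of unknown size, and the scope of its filters is unclear

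*Protocol*

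**What the plan says.** Protocol 10.1 fixes the design: "This is a three-period, three treatment, multi-site, open label, crossover study". Section 3.2 sets the safety aim: "To characterize the differential safety profiles of three daily regimens of tenofovir (oral, vaginal, and dual use").

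Section 10.2.2 lists one safety endpoint for that aim, and the Protocol Summary repeats it. The endpoint has two branches. The first is "Grade 3 or higher toxicity for systemic and local effects as defined by DAIDS AE Grading Table Version 1.0, December 2004". The second is Grade 3 or higher genital infection, pain or epithelial lesion under the Female Genital Grading Table. Two conditions follow the second branch: the event must not be directly attributable to a different cause, and it must be "judged as definitely, probably, possibly, or probably not related to the study gel, applicator, or study tablet".

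Section 8.3.3 gives five relationship categories, assessed from the DAIDS reporting manual, the product documents and clinical judgment. The endpoint admits four of them. The fifth, *not related*, applies when "the adverse event is clearly explained by another cause unrelated to administration of the study agent", with supporting documentation required for reportable events. No blinded assessment of relationship is described.

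Section 8.3.1 has sites record all adverse events "from the time of enrollment (random assignment) until study termination, regardless of severity and presumed relationship to study product".

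**The concern.** In an open-label crossover, randomised order and within-woman comparison protect the regimen contrast only if an event is counted by the same rule in each period. Here the counting rule includes a causality call. The person making it knows the regimen and assesses the event against what is in use: a tablet, a gel with applicator, or all three. The same genital event could plausibly be rated differently in a tablet-only period than in a gel or dual period. Section 10.5 recognises the open design, "In an unblinded trial, special care needs to be taken to assure that the study staff cannot control or guess assignment", but that safeguard concerns allocation, not the assessment of outcomes.

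The other-cause condition adds uncertainty because it is not defined. Section 8.3.3 describes *probably not related* as an event most likely due to something other than the study agent. The relatedness condition admits such an event, while the other-cause condition might exclude it.

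At stake is the credibility of the trial's only listed safety contrast, in a study meant to inform the design of a larger oral-versus-vaginal trial (Section 2.1).

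**Working it through.** **Plan's own figure.** None exists. Section 10.4 gives no rate or power for safety, and 10.7.2 fixes no between-regimen safety test. What follows illustrates the mechanism and does not estimate the bias.

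**Inputs.** From the protocol: 144 evaluable women, each scheduled for all three regimens (10.7.2, 10.1), and exclusion of *not related* events (10.2.2). Assumed, because the protocol gives neither: a true Grade 3 or higher rate *p* per period, equal in regimens A and B; and *d*, the share of such events dismissed in each regimen.

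**Formula.** Counted rate = *p*(1 − *d*). Counted ratio A:B = (1 − *d*_A)/(1 − *d*_B), so *p* cancels. An unfiltered count with equal true rates has ratio 1.00.

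| Dismissed, A vs B | Ratio A:B | Counted at *p* = 5% | Women of 144 |
|---|---|---|---|
| 10% vs 10% | 0.90/0.90 = 1.00 | 4.5% vs 4.5% | 6.5 vs 6.5 |
| 0% vs 10% | 1.00/0.90 = 1.11 | 5.0% vs 4.5% | 7.2 vs 6.5 |
| 10% vs 30% | 0.90/0.70 = 1.29 | 4.5% vs 3.5% | 6.5 vs 5.0 |

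In absolute terms, 0% against 10% gives a spurious difference of 0.2, 0.5 and 1.0 percentage points at *p* = 2%, 5% and 10%. For 10% against 30% it is 0.4, 1.0 and 2.0 points. Unequal dismissal creates a difference; equal dismissal does not.

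**Scope of the filters.** The sentence can be read two ways.

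- *Both branches filtered.* Every Grade 3 or higher event passes through the causality call, so both systemic and genital contrasts are exposed.
- *Genital branch only.* DAIDS-graded events count whatever their cause, while genital events must pass both conditions. Exposure is then confined to genital events, but the two kinds of harm are counted by different rules.

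The text does not settle which is meant.

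**Can an unfiltered endpoint be built from the data collected?** Yes. Section 8.3.1 captures all events whatever the grade or relationship. Section 10.1 uses each washout week to collect events that may stem from the preceding period. Three windows of six plus one weeks make 3 × 7 = 21 weeks, the whole follow-up. Each onset therefore falls in exactly one regimen's window, the windows are equal by schedule, and no causal judgment is needed to place an event.

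**The case against.** The strongest reply is that the relatedness filter is about as weak as such a filter can be. Even *probably not related* events count. Absence of gel does not by itself meet the definition of *not related*, which demands a clear alternative explanation. The tablet is also a study agent, and Section 10.3 hypothesises similar tissue levels by either route, so a genital event in a tablet period cannot be dismissed on route alone. This stands, and it limits the likely size. It does not answer the undefined other-cause condition.

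Second, many of the signs most open to expectation cannot enter the endpoint. In Appendix IV, vaginal and cervical erythema, vaginal dryness, discharge, itching, candida and bacterial vaginosis have no Grade 3. This also stands. What remains, such as severe pain or pelvic inflammatory disease, is narrower but still subject to attribution.

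Third, Section 3.2 speaks of characterising safety rather than testing it, and all-cause tables are ordinary content for an analysis plan that is not at hand. That is fair as far as tables go. The filtered definition, however, is fixed by the protocol itself, in two places.

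A reader might look for evidence of size in the powder-versus-tablet study in Section 2.6.1, where "No AEs were considered related to study drug after administration of the tablet" although all-cause events were reported by 40% on powder and 47% on tablet. The document does not support that use. All those treatment-emergent events were Grade 1, the filter there was *related* rather than anything short of *not related*, related events are given as participants and not as events, and the attributions may have been correct. The severe events in HPTN 050 (Section 13.3.1) likewise rest on a stricter product-related threshold.

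**Conclusion.** The point holds as one of exposure. The endpoint lets knowledge of the regimen influence which Grade 3 or higher events are counted, and the reach of its two conditions is ambiguous.

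A reader might infer that the comparison is biased, with genital harm inflated in gel and dual periods. The documents do not show this. Bias requires the dismissed share to differ by regimen, and nothing in the protocol gives that share, its direction or its size. The ratios of 1.11 and 1.29 rest wholly on assumed shares and equal true rates, and the ratio is 1.00 if dismissal is equal.

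Nor can a dual-to-single inflation be derived by supposing that tablet and gel are dismissed independently. Under Section 8.3.3 a clear other cause would usually dismiss both products together, and with full dependence that argument gives no inflation.

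The endpoint is secondary and the distortion may be small. The change is still worth making, because it removes the attribution step from the comparison at almost no cost.

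**What to change.** In Section 10.2.2 and the Protocol Summary, define the endpoint compared between regimens as any Grade 3 or higher adverse event under the grading table that governs it, with onset in the regimen's six-week period or the washout week that follows, regardless of judged relationship.

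Keep the count restricted by other cause and relatedness as a supportive descriptive table, and state whether its conditions apply to both branches or only to the genital-table branch.

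Keep biopsy-related events in the compared count and flag them descriptively. Biopsies are scheduled at the end of all three periods for intensive PK participants (Section 7.8.3), and removing such events would bring back the same causal judgment.

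Cost: endpoint wording in two places and one table definition. No new data, visits or participants are needed. The downside is that background events unrelated to product enter all three regimens and add some noise.

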10.3 Study Hypotheses

The study hypotheses for the primary objective are:

- There will be no differences in rates of adherence among the three study regimens
- There will be no difference in rates of acceptability among the three study regimens
- Tissue levels of PMPA will be similar irrespective of the route of administration
- Oral TDF will be associated with higher concentrations of PMPA in the blood compared to topical PMPA
- Neither tenofovir 1% gel nor oral TDF regimens will adversely impact the genital tract environment

10.4 Sample Size

Sample size/power formulas for a parallel design with two arms (i.e. two different groups of women) can be used to compute sample size/power. Then, this sample size resulting from the assumption of independent groups can be adjusted to reflect that there will be intra-woman correlation in the crossover design. The sample size adjustment can be obtained by this formula:

N' = N (1 - rho)/2

where N' is the sample size for a crossover study, N is the total number of women required in a parallel design with two arms (N/2 in each arm) and rho is the correlation between responses within a single woman during different periods (intra-woman correlation).

For the adherence endpoint, we use preliminary data from HPTN 059 to estimate the standard deviation (SD) of daily gel use and make the assumption that the standard deviations of adherence to daily oral use and of adherence to dual use are similar to that for daily gel use. From the first 4 weeks and the first 8 weeks of daily gel use observed in HPTN 059, we have observed a SD of 11% and 16%, respectively (note that we do not have data in HPTN 059 for the first 6 weeks). Therefore, we use a conservative estimate for the SD for the first 6 weeks of 20%.

To our knowledge, there are no data available for estimating rho. However, it is highly likely that this correlation will be positive and large. The following table gives the power to detect various differences in adherence with a sample size of 144 evaluable women:

	Rho					
	0.0	0.3	0.5	0.7		
Minimum Detectable Absolute						
Difference in Adherence Between Any						
Two Regimens						
2.5%	18%	24%	32%	49%		
5.0%	56%	72%	85%	97%		
7.5%	89%	97%	99%	>99%		

Table 13: Minimum Detectable Difference in Adherence

If there is no intra-woman correlation for adherence, the study will have \geq 89% power to detect absolute differences between the different study drug regimens of at least 7.5% with a two-sided alpha of 5%. Assuming a moderately high intra-woman correlation of 0.5 for adherence, the study will have \geq 85% power to detect an absolute difference of at least 5.0% with a two-sided alpha of 5%.

For the acceptability endpoint, based on previous studies we expect to observe acceptability > 95%, which equates to \leq 5% of women reporting they would be "unlikely" to use the study product in the future. Power is computed by using formulas appropriate for the McNemar test (formula 3.1 in Ezzet and Whitehead).¹² For the computations, we assume that the pooled acceptability for two regimens is 90% giving a probability of 18% that a woman has two different outcomes in two different periods (i.e. finds one product acceptable and the other not acceptable). Under this assumption, and assuming a 2-sided test with α =0.05, with 144 evaluable women we have 80% power to detect a log-odds ratio between acceptability rates in two groups of 1.10. If acceptability in one group is 95%, this corresponds to being able to detect a 13% difference (i.e., 5% versus 18% being "unlikely" to use study product in the future) in acceptability between different study product regimens. If acceptability in one group is 98%, this corresponds to being able to detect a 5% difference (i.e. 2% versus 7% being "unlikely" to use study product in the future) in acceptability between different study product regimens. Although the primary analysis for this endpoint will not rely on the McNemar test (see details in Section 10.7.2), the above computations provide a good approximation given that the range of individual acceptabilities observed in previous studies is rather homogenous. This leads to a small degree of heterogeneity; therefore negligible sample size adjustment is needed for the use of random effects model.

Finally, for the secondary endpoint assessing condom use rates during the different drug regimens, we use preliminary data from HPTN 035 to estimate the SD of percent condom use and make the assumption that the SDs of condom use for daily oral use and dual use are similar to that for daily gel use. From the first 2028 participants enrolled in HPTN 035 we have observed a condom use rate of 72% with a SD of 34% and we use this estimate of the SD for the power calculations.

Again, to our knowledge, there are no data available for estimating rho. However, it is highly likely that this correlation will be positive and large. The following table gives the

power to detect various differences in condom use rates with a sample size of 144 evaluable women:

	Rho					
	0.0	0.3	0.5	0.7		
Minimum Detectable Absolute						
Difference in Condom Use Between						
Any Two Regimens						
2.5%	9%	11%	14%	21%		
5.0%	24%	32%	42%	62%		
7.5%	46%	61%	75%	93%		
10%	70%	85%	94%	>99%		

 Table 14: Minimum Detectable Difference in Condom Use

If there is no intra-woman correlation for condom use, the study will have low power to detect absolute differences in condom use rates of <10% between the different study drug regimens. Assuming a moderately high intra-woman correlation of 0.5 for condom use, the study will have \geq 75% power to detect an absolute difference of at least 7.5% with a two-sided alpha of 5%.

Methods for sample size estimates for the sparse sampling population PK analysis are not available. However, experience indicates that 144 participants, especially when each contributes a pair of specimens the same dosing interval, should provide robust PK parameter estimates.

The more intensive PK sampling to be done at the domestic sites will involve 72 women. Based on data from Gilead in the package insert¹, the coefficient of variation for C_{max} , AUC, and total clearance (CI/F) are 30%, 30%, and 11%, respectively. With 72 participants, assuming no intra-individual correlation, we have 90% power to detect a 0.38 SD unit difference between any two regimens being compared. This represents a 14% difference in C_{max} and AUC and a 5% difference in total clearance (CI/F). If one assumes some correlation within a participant between periods – a very reasonable assumption – these estimates would be even lower. However, because we are using fewer sample points than used in the Gilead tenofovir studies in which the parameter estimates and SDs were determined, we expect that this may increase the variability of the estimates, so we will make no adjustments for intra-participant correlations.

In HPTN 050, blood levels after vaginal tenofovir were too low to allow variance estimates needed for sample size calculations since only one-third of the women had detectable levels of tenofovir in their blood following any given dose. Comparisons of oral and dual formulation arms will rely on imputations of values that are below the assay limits of quantitation which will have the effect of actually reducing the variance of the data which may falsely increase the apparent power of the study design.

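### The detectable acceptability differences in Protocol 10.4 do not follow from the stated log-odds ratio of 1.10, and the 2% versus 7% case cannot have the 18% discordance behind the 80% power

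*Protocol*

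**What the plan says.** The relevant text is the acceptability paragraph of Protocol 10.4 (Sample Size). It expects acceptability above 95%, uses a power formula for the McNemar test, and sets these inputs:

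- Pooled acceptability: "we assume that the pooled acceptability for two regimens is 90" per cent, "giving a probability of 18% that a woman has two different outcomes in two different periods".
- Test: "assuming a 2-sided test with α =0.05".
- Result: "with 144 evaluable women we have 80% power to detect a log-odds ratio between acceptability rates in two groups of 1.10".

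It then turns that one effect size into two absolute contrasts in the proportion of women unlikely to use the product in future. When one regimen has 95% acceptability, "this corresponds to being able to detect a 13% difference (i.e., 5% versus 18% being" unlikely. When one regimen has 98% acceptability, "this corresponds to being able to detect a 5% difference (i.e. 2% versus 7% being" unlikely. The same paragraph notes that the primary analysis will be a random-effects model rather than McNemar, and treats the McNemar result as a good approximation because heterogeneity between women is small.

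**The concern.** Both contrasts are presented as the same log-odds ratio of 1.10, yet they have different odds ratios, and neither equals exp(1.10). Separately, the 80% power depends on 18% of women giving two different answers, which is more than rates of 2% and 7% allow.

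Acceptability is a primary endpoint (10.2.1) with a stated hypothesis of no difference (10.3), and the rationale (2.7.2) ties it to the design of MTN-003. A null result will be read against the detectable differences in 10.4. The 98% case is the one of the two that lies in the expected range above 95%. There, a reader would take a 5-point difference as detectable with 80% power.

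**Working it through.** **Inputs, all from 10.4:** N = 144, two-sided alpha 0.05 (z = 1.960), power 80% (z = 0.842), discordance ψ = 2 × 0.90 × 0.10 = 0.18, log-odds ratio θ = 1.10.

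**1. Reproduce the stated effect size.** With the log-odds form of McNemar power, θ = 2(1.960 + 0.842)/√(Nψ). Here Nψ = 144 × 0.18 = 25.92, so θ = 1.1006. At θ = 1.10 the power is Φ(θ√(Nψ)/2 − 1.960) = 79.96%. The headline figure is therefore right under this formula.

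**2. Translate it.** exp(1.10) = 3.00.

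| Starting rate | Rate at log-odds ratio 1.10 | Difference | Printed pair | Log-odds ratio of printed pair |
|---|---|---|---|---|
| 5% | 13.7% | 8.7 points | 5% v 18% | 1.43 (odds ratio 4.17) |
| 2% | 5.8% | 3.8 points | 2% v 7% | 1.31 (odds ratio 3.69) |

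As a cross-check, 18% discordance split 3:1 is 13.5% against 4.5%, a difference of 9.0 points, not 13.

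Rounding of the second rate gives ranges of 1.39 to 1.46 and 1.23 to 1.38. Reading 1.10 as a log risk ratio gives 15.0% and 6.0%. Neither recovers the printed pairs.

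**3. Is 18% discordance possible?** For rates p and q, discordance lies between |p − q| and p + q.

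- 5% v 18%: 13% to 23%, so 18% is possible.
- 2% v 7%: 5% to 9%, so 18% is impossible. Independence gives 0.02 × 0.93 + 0.07 × 0.98 = 8.72%, or about 12.6 discordant women instead of 25.9. The 2pq rule used for the 18%, applied at 95.5% pooled acceptability, gives 8.6%.

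**4. Power at each pair's own discordance under independence, N = 144.** The unconditional normal formula is Φ[(δ√N − 1.960√ψ)/√(ψ − δ²)], with δ the difference in rates. The exact and uncorrected McNemar tests were enumerated over the number of discordant women.

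| Pair | ψ | Exact | Uncorrected | Unconditional normal | Log-odds formula |
|---|---|---|---|---|---|
| 5% v 18% | 21.2% | 92% | 95% | 93% | 98% |
| 2% v 7% | 8.72% | 44% | 53% | 53% | 64% |

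Log-odds formula for 2% v 7%: 1.305 × √12.56/2 − 1.960 = 0.352, and Φ(0.352) = 64%.

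**5. Contrasts that do reach 80% under independence.**

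- Log-odds formula: about 5% v 13.9% (log-odds ratio 1.12) and 2% v 8.2% (1.48).
- Unconditional normal formula: about 5% v 15% and 2% v 10%.

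**The case against.** **The power figures for 2% versus 7% are conditional.** 10.4 never names independence for acceptability; it is inferred from 18% = 2 × 0.9 × 0.1. For adherence and condom use the same section calls within-woman correlation very probably large and positive. Such correlation lowers discordance and raises power at fixed rates. Taking correlations of 0.2 and 0.4 purely as assumptions, power for 2% versus 7% becomes 52% or 63% (exact), 63% or 78% (uncorrected) and 78% or 96% (log-odds formula). At the 5% discordance floor, where every discordant woman moves the same way, it is 73% to 93% depending on the test version. This objection stands: a reader might infer that the true power is some fixed figure well below 80%, and the documents do not support that. The objection does not rescue the printed claim, which rests on 18% discordance.

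**The log-odds ratio might be subject-specific.** This does not help. 10.4 assumes little heterogeneity, and heterogeneity would pull the marginal odds ratio below 3.0, not up to 4.17.

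**The starting rates might be rounded too.** Treating 2% as rounded would widen the second range to 1.00 to 1.67, which includes 1.10. But 2% and 5% are chosen inputs, and the 5% versus 18% pair would still lie at 1.29 to 1.57.

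**The formula is inferred.** 10.4 cites a formula in a paper that is not at hand. The agreement at 1.1006 supports the log-odds form without proving it. The translation error and the 9% ceiling do not depend on it.

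**The 5% versus 18% statement is conservative.** That is correct: the study can detect that difference with more than 80% power.

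**Conclusion.** The point holds. Two errors follow from the inputs in 10.4 without further modelling: a log-odds ratio of 1.10 means 5% versus 13.7% and 2% versus 5.8%, not the printed pairs; and rates of 2% and 7% cannot produce 18% discordance, so the 80% power does not apply to them.

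The errors run in opposite directions. The 5% versus 18% statement understates sensitivity (92% to 98% power under independence). The 2% versus 7% statement overstates it under the same assumption (44% to 64%, by test version), with higher values if a woman's answers are positively correlated. All these figures approximate a random-effects analysis.

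Two further inferences should be resisted. A reader might conclude that the sample size is inadequate; 10.4 fixes no target acceptability difference that 144 women must detect, so that does not follow. A reader might also guess how the printed differences arose, since 13.7% and 5.8% lie near 13 and 5; they round to 14 and 6, and the document shows no working, so the cause remains unknown.

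**What to change.** Rewrite the translation sentences in the acceptability paragraph of 10.4:

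- Name one power formula and state the within-woman correlation assumption.
- Recompute discordance for each pair of rates instead of carrying 18% throughout.
- Replace the two contrasts. Under independence, give either 5% v 13.9% and 2% v 8.2% (log-odds formula, which reproduces 1.10) or about 5% v 15% and 2% v 10% (unconditional McNemar normal formula). Do not mix the two: 2% v 8%, for example, falls short of 80% under the exact, uncorrected and log-odds versions alike (57% to 77%).
- Remove the 13-point difference. Remove the 80% power claim for 2% versus 7%, or give its conditional power with the assumption and test named.

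The cost is protocol wording only. Sample size, conduct and planned analysis stay as they are.
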